11.2.2. Reporting Serious Adverse Events to Division of Cancer Prevention

11.2.2.1 The Lead Organization and all Participating Organizations will report SAEs on the DCP SAE form found at <http://prevention.cancer.gov/clinical-trials/clinical-trials-management/protocol-information-office/pio-instructions-and-tools/2012-consortia>.

11.2.2.2 Contact the DCP Medical Monitor by phone and email within 24 hours of knowledge of the event.

Medical Monitor - Division of Cancer Prevention

[name], M.D.  
Lung and Upper Aerodigestive Cancer Research Group  
Division of Cancer Prevention, NCI, NIH  
[name]  
[name] (For FedEx, use [name])  
[contact]

E-mail: [[contact]](mailto:[contact])

The following information will be included when calling the Medical Monitor:

- Date and time of the SAE
- Date and time of the SAE report
- Name of reporter
- Call back phone number Affiliation/Institution conducting the study DCP protocol number
- Title of protocol
- Description of the SAE, including attribution to drug and expectedness

University of Wisconsin will alert the University of Washington, IND sponsor by one of the methods below:

[name], M.D.  
University of Washington  
IND Sponsor  
[[contact]](mailto:[contact])  
[contact]

11.2.2.3 The Lead Organization and all Participating Organizations will email written SAE reports to DCP's Regulatory Contractor CCS Associates, Inc. (CCSA; [contact]) at [[contact]](mailto:[contact]) within 48 hours of learning of the event using the fillable PDF SAE Report Form.

11.2.2.4 The DCP Medical Monitor and UW IND Sponsor will determine which SAEs require Food and Drug Administration (FDA) and National Institutes of Health Office of Biotechnology Activities (NIH OBA) submissions.

11.2.2.5 The Lead Organization and all Participating Organizations will comply with applicable regulatory requirements related to reporting SAEs to the IRB/IEC.

### 11.2.3 Follow-up of SAE

Site staff will send follow-up reports as requested when additional information is available. Additional information will be entered on the DCP SAE form in appropriate format. Follow-up information will be sent to DCP as soon as available. SAEs will be followed until resolution to baseline or stable.

### 11.2.4 Reporting to other agencies

Procedure for reporting serious adverse events:

- a. Identify the “System Organ Class” of the adverse event as defined above using CTCAE v4.0. Attribution must be assigned by the study doctor.
- b. After appropriate medical intervention has been instituted, the PI or his/her designee will be notified within the first 24 hours of the event.
- c. File appropriate reports immediately by phone/fax with appropriate agencies
- d. Notify the patient’s primary doctor or referring doctor within a medically appropriate timeframe, depending on the severity of the adverse event.
- e. Submit written reports to appropriate agencies.
- f. Document the adverse event in the patient’s research file, using a progress note to describe the event and treatment, if appropriate.
- g. File copies of all forms/correspondence relating to the adverse event in the patient’s research file.

FDA – Serious adverse events will be reported by UW, [name], (IND Sponsor) per 21 CFR 312.32 using the narrative format and/or MedWatch Form 3500A.

NIH OBA - any SAE will be reported per Appendix M. SAEs undergoing expedited reporting to the FDA as IND safety reports will be reported to OBA in the same timeframe.

Institutional Biosafety Committee (IBC) – IBC should be notified at the same time as NIH OBA. This study will go through UW and UWI’s IBC and each group will report their institution’s committee using the documentation submitted to the FDA.

IRB/IEC–UW and UWI will follow the current AE reporting policy of the institutional and NCI central IRB.

UW CRC - The UW CRC will receive copies of the documents submitted to the FHCRC/UW CC IRB within 7-10 calendar days.

FHCRC Biologic Production - The FHCRC Biologic Production will receive copies of the documents submitted by [name], IND Sponsor, using either the narrative format, the MedWatch Form 3500A, or using the Genetic Modification Clinical Research Information System within 7-15 calendar days.

UWI Chemoprevention Consortium Data Safety Monitoring Board (DSMB) – the UW will follow the UWI Consortium DSMB.

### **11.3 Long-Term Follow-Up (LTFU)**

Long-term follow-up will continue through review of clinical notes, lab values, and imaging reports requested annually from the participant’s primary oncologist or primary care provider.

Each site will be responsible for requesting the selected medical records from their participants’ primary oncologist or primary care provider. The collected information will be abstracted to record any possible autoimmune reactions and relevant health status.

This information will be reported annually to the FDA in order to satisfy their LTFU reporting requirements.

## **12. STUDY MONITORING**

### **12.1 Data Management**

All of the procedures outlined in the University of Wisconsin Chemoprevention Consortium standardized Data Management Plan (approved 09/23/2019) will be followed in this protocol. Please refer to this document for additional details on data management procedures. This plan will be followed until all participants have completed the 6-month follow-up visit.

Long-term follow-up data will be kept and managed by University of Washington per their institutional policy. Systems are in place to ensure data integrity. Once notes are received, a University of Washington Clinical Research Staff Member, designated by the IND Sponsor, will review the summary and report relevant autoimmune and relevant health status data in the database.

## **12.2 Case Report Forms**

All data entry until completion of the 6 month follow-up visit will be performed by the Consortium Lead Organization (or CLO, the University of Wisconsin) staff. Electronic CRF (eCRF) screens will be created in OnCore. CLO staff will enter data into OnCore and transfer to Federal Security Compliant formats for transmission to DCP according to pre-established DCP standards and procedures. Amended CRFs will be submitted to the DCP Protocol Information Office for review and approval.

This study will report clinical data using the CLO database OnCore which is a web-based clinical trials/database. OnCore will be the database of record for the protocol and subject to NCI and FDA audit. All OnCore data entry including the 6 month follow-up visit will be performed at the CLO where staff is trained in OnCore per our DMP and applicable regulatory requirements such as 21 CFR; Part 11.

Data collected for LTFU is entered into a database that is password protected, has an audit trail and only allows limited access to patient information. Only research staff that has been designated by the IND Sponsor will have access to the LTFU data in the database. The database is regularly backed-up on tape from our secured server. This server network is HIPAA compliant and backed up to a tape on a regular basis so we may recover data that is lost for any reason. This is all managed according to HIPAA regulations.

## **12.3 Source Documents**

In order to standardize the collection of study data, the University of Wisconsin (CLO) and the University of Washington will work together to create Visit Guides and Source Document Worksheets to ensure that all required data elements are captured. These documents will be used to supplement data collected on primary clinical source documents. All data reported must be documented either on a separate source document found in the patient's medical record or on the Visit Guides and Source Document Worksheets. All source documents must be signed by the staff that collected or elicited the information in the source documents. Source documents will be submitted to the CLO (either by fax, or e-mail) for entry into the OnCore database. Primary clinical source documents will be de-identified and relabeled with the patient's PID number prior to submission. All data is due at the CLO within 10 business days of each study visit.

Source documents for annual long-term follow-up will be submitted to the University of Washington and entered into the database. All data will follow the above de-identification process.

## **12.4 Data and Safety Monitoring Plan**

All of the procedures outlined in the University of Wisconsin Chemoprevention Consortium standardized Data and Safety Monitoring Plan (approved 03/20/2018) as well as the Master Data and Safety Monitoring Plan: Addendum #1 will be followed in this protocol. The UW Chemoprevention Consortia Data and Safety

Monitoring Committee meet every 6-12 months to review all data from ongoing consortium studies. Members review pooled, unblinded safety data to assess ongoing human subject's safety. Data from this study will be monitored through the end of the 6 month follow-up visit by UW Chemoprevention Consortia DSMB. Data collected as part of long term follow-up will be monitored by the University of Washington.

## **12.5 Sponsor or FDA Monitoring**

The NCI, DCP (or their designee), pharmaceutical collaborator (or their designee), or FDA may monitor/audit various aspects of the study. These monitors will be given access to facilities, databases, supplies and records to review and verify data pertinent to the study.

## **12.6 Record Retention**

Clinical records for all patients, including CRFs, all source documentation (containing evidence to study eligibility, history and physical findings, laboratory data, results of consultations, *etc.*), as well as IRB records and other regulatory documentation will be retained by the Investigator in a secure storage facility in compliance with Health Insurance Portability and Accountability Act (HIPAA), Office of Human Research Protections (OHRP), Food and Drug Administration (FDA) regulations and guidance's, and NCI/DCP requirements, unless the standard at the site is more stringent. The records for all studies performed under an IND will be maintained, at a minimum, for two years after the approval of a New Drug Application (NDA). For NCI/DCP, records will be retained for at least three years after the completion of the research. NCI will be notified prior to the planned destruction of any materials. The records should be accessible for inspection and copying by authorized persons of the Food and Drug Administration and OHRP.

## **12.7 Cooperative Research and Development Agreement (CRADA)/Clinical Trials Agreement (CTA)**

N/A

## **13. STATISTICAL CONSIDERATIONS**

### **13.1 Study Design/Description**

This is a phase I non-randomized, dose - escalation study of safety and immunogenicity of a triple antigen vaccine. The study population consists of relatively healthy and stable patients with history of breast cancer.

Patients will be assigned sequentially to one of three arms defined by vaccine dose. Patients will be accrued to Arm 1 first, then Arm 2, and Arm 3.

- Arm 1: WOKVAC (150 mcg) with rhuGM-CSF (100 mcg); administered i.d. every month for 3 total doses.
- Arm 2: WOKVAC (300 mcg) with rhuGM-CSF (100 mcg); administered i.d. every month for 3 total doses.
- Arm 3: WOKVAC (600 mcg) with rhuGM-CSF (100 mcg); administered i.d. every month for 3 total doses.

If there is sufficient evidence (please see Section 8.5.1. Criteria for Premature Study Termination) to suggest the Arm 1 dose is safe; the Arm 2 cohort of up to 12 patients will be enrolled. If the Arm 2 dose is also regarded as sufficiently safe, the Arm 3 cohort of up to 12 patients will be enrolled. If the Arm 3 dose appears safe, the immunologic efficacy among three dose groups will be examined to determine the recommended phase 2 dose for further cancer prevention studies. For the phase 2 study, safety and immunologic efficacy decisions will be made on the evaluation of data from the three possible doses.

After the Arm 3 dose, key study personnel in concert with the NCI/DCP staff will review the immunologic efficacy data along with safety with other laboratory findings to make a decision on an appropriate phase 2 dose.

### **13.2 Randomization/Stratification**

N/A.

### **13.3 Accrual and Feasibility**

The study will accrue 30 evaluable patients with up to 12 patients in each dose arm. We anticipate up to 15% of enrolled patients may fail to receive all three vaccinations and the 1 month post vaccine follow-up.

For information regarding the study population (including gender and minority considerations) please see Section 4.3 Inclusion of Women and Minorities.

In order to meet the primary objective of this study, AE information is collected at each of the study visits and reviewed by the study team on a regular basis. If patients are unable to complete to the one month post vaccination follow-up visit, AE information may be collected by phone if possible. For secondary objectives, the research samples will be batched after each cohort to achieve consistency in the assays.

When we batch the research samples we will run the baseline time point and post vaccine time point(s) for a patient (usually 4-5 patients at one time). With this we are looking at results of an individual (comparing their IFN-g response to their baseline) therefore the results can be analyzed together.

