### **10.2 Collection and Handling Procedures**

Approximately 15 mls of blood will be drawn for clinical labs at each study visit.

Approximately 200 mls of blood for immunologic monitoring will be collected at the first vaccination visit, as well as, 1 month (28+7 days) and 6 months (168 ± 14 days) after the last vaccine. Research blood will be transported at ambient temperature until processed by the UW IML within approximately 34 hours of the blood draw. Specimens and plasma are then stored at approximately -80°C until use. Serum will be processed at each site and stored in a -80°C freezer and will be shipped to IML in batches. When whole blood is to be shipped overnight to the IML, it cannot be drawn on a Friday or a day prior to a holiday. Blood cannot be drawn or shipped on Friday or day prior to a holiday if it is being shipped overnight.

ELISPOT and FACS will be done on research samples in batches by the UW IML. Serum samples will be stored and analyzed at the end of the study.

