### **13.5 Secondary Objectives, Endpoints, Analysis Plans**

- To determine the immunogenicity of WOKVAC Th polyepitope plasmid based vaccine in patients with breast cancer at 3 escalating doses.
- To evaluate for the presence of a Th2 immune response by antibodies against the WOKVAC antigens
- To determine whether a WOKVAC Th polyepitope plasmid based vaccine elicits a persistent memory T cell response.
- To evaluate whether WOKVAC vaccination modulates T regulatory cells (Treg) and myeloid derived suppressor cells (MDSC).
- To determine a recommended phase 2 dose for further breast cancer prevention studies.
- To assess the long-term effects of 3 escalating doses of a deoxyribonucleic acid (DNA) plasmid

based vaccine encoding three breast cancer antigens (IGFBP-2, HER2, and IGF-1R) in patients with breast cancer, for 5 years from enrollment to satisfy the evaluation requirements for the Food and Drug Administration (FDA)

Immune responses as measured by IFN-g ELISPOT will be summarized with mean and standard deviation or median and range over time, the change over time will be summarized with graphs, and also analyzed using linear mixed-effects regression models with normalizing transformation if necessary. Each patient would be given a value at each immune evaluation that is the sum of the median response to HER2, IGFBP-2 or IGF1R, and a composite median would be calculated for each WOKVAC dose level.

Antibody immunity will be assessed as an additional measure of a Th2 response. A humoral immune response will be measured by ELISA and serum antibody avidity for IGFBP-2, HER2, and IGF-1R (using ELISA) to determine an avidity index (AI) before and after vaccination. Low avidity antibodies will have an AI <30%, moderate avidity antibodies 30-50% and high-avidity antibodies 51-100%. Patients will be considered to have developed an antibody response if antigen specific IgG antibodies are both detectable and have moderate to high avidity.

Memory T cell response will be summarized with proportion over time, and the change over time will be summarized with bar charts, and analyzed using generalized linear mixed effects regression models with suitable link function.

Treg cell, and MDSC levels will be summarized with mean and standard deviation or median and range over time, the change over time will be summarized with graphs, and analyzed again using linear mixed-effects regression models with normalizing transformation if necessary.

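### ELISPOT and flow cytometry runs are nested within dose arm, and the dose-response regression in 13.5 names no baseline term although 13.3 rests pooling on the same-run baseline

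*Combined protocol and SAP*

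**What the plan says.** **Accrual and assay timing.** Section 13.1: "Patients will be accrued to Arm 1 first, then Arm 2, and Arm 3". The same section uses cohort to mean a dose arm ("the Arm 2 cohort of up to 12 patients will be enrolled"). Section 10.2: "ELISPOT and FACS will be done on research samples in batches by the UW IML". Section 13.3 adds that "the research samples will be batched after each cohort to achieve consistency in the assays". For serum, 10.2 differs: "Serum samples will be stored and analyzed at the end of the study".

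**Why results may be pooled.** On the make-up of a run, 13.3 says "we will run the baseline time point and post vaccine time point(s) for a patient (usually 4-5 patients at one time", and then: "With this we are looking at results of an individual (comparing their IFN-g response to their baseline) therefore the results can be analyzed together".

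**How doses are compared.** Section 13.5 defines the IFN-g summary as a level: "Each patient would be given a value at each immune evaluation that is the sum of the median response to HER2, IGFBP-2 or IGF1R". A composite median is then taken for each dose. Change over time is modelled with mixed-effects regression for IFN-g, Treg and MDSC, and with a generalized linear mixed model for memory T cells. The comparison between doses is a separate linear dose-response regression, with 0.80 power for an effect size R²/(1−R²) of 0.281 at N = 30. Its outcome, visit and any baseline term are not given.

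**Standing.** Section 13.5 calls these analyses descriptive and the tests advisory. Section 13.9 expects immunogenicity to be the endpoint that takes the vaccine forward and sets out to find the dose that stimulates immunity best.

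**The concern.** With arms filled in sequence and samples assayed after each arm, no run is described that mixes doses. A plate, reagent or operator effect that moves all results in a run up or down therefore moves results for one dose only. Comparing post-vaccine levels between doses cannot tell such a shift from a dose effect.

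The design already holds a partial safeguard: each patient's baseline is assayed in the same run as the post-vaccine samples. Section 13.3 relies on this when it says the results can be pooled. The safeguard works only if the dose comparison uses that baseline, and 13.5 does not say that it does. At stake is the immunogenicity evidence that feeds the recommended phase 2 dose. Ranking doses by level is exposed to a run shift whether or not a test is done.

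**Working it through.** **1. The plan's own figure.** Inputs from 13.5: f² = 0.281, N = 30, level 0.05. With dose as the only predictor, df = 1 and 28, critical F = 4.196 and noncentrality λ = f² × N = 0.281 × 30 = 8.43. Power is 0.8003, so the stated 0.80 is right. The effect size is defined on the whole-model R²; an overall test with two predictors gives 0.69. The figure therefore corresponds to a model with dose alone.

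**2. How a run effect enters.** Assumptions, since the documents give no run variance or baseline-post correlation: 10 patients per arm, two runs of 5 per arm, patient SD 1, additive run SD s, correlation ρ. Take s = 0.5 and ρ = 0.5.

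- *Post-vaccine level alone.* True variance of an arm mean: 1/10 + 0.25/2 = 0.225. Ordinary regression assumes about (1 + 0.25)/10 = 0.125. Ratio 1.8. The critical t of 2.048 acts like 2.048/√1.8 = 1.53, which is exceeded by chance about 14% of the time.
- *Baseline as covariate.* The baseline slope is roughly (ρ + s²)/(1 + s²) = 0.75/1.25 = 0.6, so about 0.4 of the run effect remains. Remaining patient variance: 1 + 0.36 − 2 × 0.6 × 0.5 = 0.76. True arm-mean variance: 0.076 + (0.4 × 0.5)²/2 = 0.096. Assumed: (0.76 + 0.04)/10 = 0.080. Ratio 1.2, giving about 7%.
- *Same-run change.* The run effect cancels if it is additive on the analysis scale.

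**3. Simulation** (20,000 trials per setting). Type I error of the nominal 0.05 dose test:

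| Run SD / patient SD | Level alone | Baseline covariate, ρ = 0.3 | Baseline covariate, ρ = 0.5 | Change |
|---|---|---|---|---|
| 0 | 0.05 | 0.05 | 0.05 | 0.05 |
| 0.33 | 0.10 | 0.07 | 0.065 | 0.05 |
| 0.5 | 0.15 | 0.09 | 0.075 | 0.05 |
| 0.65 | 0.20 | 0.11 | 0.085 | 0.05 |

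Equal dose spacing and 150/300/600 spacing give the same picture. With runs of 4, 3 and 3 per arm, levels alone give about 0.11 at run SD 0.5.

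**4. Cost when there is no run effect** (power at f² = 0.281):

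| ρ | Level alone | Baseline covariate | Change |
|---|---|---|---|
| 0.3 | 0.80 | 0.82 | 0.66 |
| 0.5 | 0.80 | 0.89 | 0.80 |

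**5. Zero baselines** (assumed Poisson counts, log(count + 1), ρ = 0.5, zeros in 0 / 4 / 10 / 33% of patients). Power with no run effect: level 0.79 / 0.79 / 0.79 / 0.79; covariate 0.87 / 0.84 / 0.82 / 0.79; change 0.77 / 0.67 / 0.57 / 0.38. Type I error at run SD 0.5: level 0.15 / 0.15 / 0.15 / 0.16; covariate 0.075 / 0.087 / 0.113 / 0.138. The 33% case echoes the non-response figure in 2.3.3, which concerns single antigens; a sum over three antigens may be zero less often.

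**The case against.** The strongest reply is that the plan already points to a baseline comparison. Section 13.3 states it for IFN-g and designs the runs around it. Section 13.9 limits immune evaluation to patients with baseline and 1-month draws, which largely supplies the visit. Section 13.6 requires more than a doubling from baseline where immunity pre-exists, and 13.5 models change over time. On this view only a cross-reference is missing. Further, the tests gate nothing, the phase 2 dose comes from a joint review with safety data, one laboratory runs all research samples, and every magnitude above is assumed.

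Most of this stands. A reader might infer that 13.5 contradicts 13.3. It does not: 13.5 is silent on the point. A reader might also infer that the dose comparison will be made on post-vaccine levels alone. The documents do not say so, and that reading fits 13.3, 13.6 and 13.9 least well.

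What the reply does not remove is that the one analysis comparing doses has no stated baseline term and is powered with dose alone. The mixed models over time state no dose-by-time term. The responder rule uses baseline only in patients with pre-existent immunity; for the others an absolute 1:20,000 threshold applies.

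**Conclusion.** The point holds as an omission in a descriptive secondary analysis. Cellular assay runs are nested within dose, and 13.5 does not carry the same-run baseline into its dose-response regression. The 0.80 power is correct as stated.

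The size is illustrative. At an assumed run SD of half the patient SD and correlations of 0.3 to 0.5, type I error is about 0.15 on levels, 0.075 to 0.09 with baseline as covariate, and 0.05 on change. With no run effect, the covariate gives power of 0.82 to 0.89 against 0.80. It therefore improves on raw levels if there is a run effect and loses nothing in these settings if there is none. The improvement shrinks as zero baselines become common.

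Two stronger conclusions are tempting and not supported. One is that run effects are known to distort the dose ranking: the documents give no run variance. The other is that change from baseline should be the primary analysis: it removes an additive run effect fully, but loses power when the baseline-post correlation is low or baselines are zero.

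**What to change.** In 13.5, specify the dose-response regression as the 1-month value, on the transformed scale if needed, on dose with the same-run baseline value as covariate. Apply this to the IFN-g composite, Treg and MDSC, and use the matching baseline adjustment for memory T cells. Report change from the same-run baseline by dose beside the raw medians, as a supporting analysis and not the primary one.

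State two limits alongside. The covariate reduces a run effect but does not fully remove it, and the absolute 1:20,000 threshold stays exposed to run shifts.

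The cost is wording and one residual degree of freedom (28 to 27). No extra samples, visits or assays are needed, because both draws are already required and assayed together. Batching after each cohort stays as it is, since 13.10 calls for the cellular endpoints to be analysed after each dose level. Recording the run of each sample is an optional addition that would let a run effect be examined later.
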